2.2.2 Secondary Endpoint*

- VAS, n, PACU and postoperative days 1-3 (twice daily)
- BPS, n, PACU and postoperative days 1-3 (twice daily)
- Time until anesthetic emergence (min)
- Delirium incidence (%)
- Positive depression screen incidence (%)
- Positive anxiety screen incidence (%)
- Change in affect scores (n)
- Change in Trail Making Test scores (n) from baseline

^{*}Tertiary assessments are listed in section 7.2

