Inclusion criteria: Adult (≥18 years old) patients undergoing non-cardiac, non-neurologic, non-major vascular surgery (i.e., below the diaphragm).

Exclusion criteria: Emergency surgery, cognitive impairment precluding capacity for informed consent, uncontrolled cardiac arrhythmias, seizure disorders, intolerance or allergy to caffeine, history of diabetes, preoperative opioid use, pheochromocytoma, acute liver failure, enrolled in conflicting research study, pregnancy, breastfeeding, severe visual or auditory impairment (may hinder cognitive function testing), and patients unable to speak English.

Perioperative and anesthetic procedures: Patients will be consented and enrolled at preoperative clinic locations, where a medical and psychiatric history will be taken and baseline assessments will be administered (described further below). After enrollment, patients will also complete a caffeine intake survey to quantify baseline caffeine consumption. On the day of surgery, baseline cognitive function testing (TMT) will take place in the preoperative holding area. Subsequently a 16-channel wireless EEG system (Cognionics, Inc.) will be applied to the scalp for continuous monitoring during surgery and the perioperative period. Once in the operating room, anesthetic induction and maintenance will proceed as deemed clinically appropriate by the anesthesia team. At the beginning of surgical closure, the study drug will be given via intravenous infusion over 60 minutes (placebo vs. caffeine, 200 mg) in a triple-blinded fashion: the anesthetic team, research staff, and patient will all be blinded to the intervention. Infusion of this dose over a 60-minute period has been safely described, without significant side effects or adverse events noted.^{28,32} A member of the research team will remain in the operating room to monitor drug infusion and collect data regarding timing of anesthetic discontinuation and emergence; this will aid methodological rigor and data validation for the study. The EEG sensors will remain in place during the operation and emergence from anesthesia; they will then be removed shortly after PACU arrival. One hour after the caffeine infusion finishes, pain and cognitive function measures will be assessed.

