Neurocognitive assessments: Time from surgical closure to anesthetic emergence will be calculated by the study team. (minutes). The Trail Making Test will be used to assess perioperative cognitive function. The TMT is a validated, reliable test that assesses four cognitive domains relevant to the perioperative setting: processing speed, attention, visual scanning, executive function, and working memory. The TMT is administered in a standardized fashion using paper and pencil and takes approximately 5 minutes to complete. This is a feasible strategy in the perioperative setting to obtain comprehensive cognitive function data (e.g., attention, executive function) in a relatively short period of time, and normalized population data are available for comparisons. The test will be administered preoperatively and one hour after the caffeine infusion has completed in conjunction with pain assessments. Changes (n) in standardized scores from baseline will be calculated, and final standardized scores (n) will also be calculated and reported in the event that baseline scores are unable to be obtained (given the time-constraints present in the preoperative setting, it might not be possible to achieve baseline cognitive function scores in all patients).

Neuropsychological assessments: The Hospital Anxiety and Depression Scale (HADS)³⁸ will be used to assess for active depression and anxiety symptoms in each group. These assessments will take place at baseline and after the last inpatient assessment on postoperative day 3. Scores ≥8 for the anxiety (HADS-A) and depression (HADS-D) subscales will be considered positive screens.⁵¹ The Positive and Negative Affect Schedule

(PANAS)³⁹ will be used to characterize mood and affect at the same time points as depression and anxiety screening (baseline and postoperative day 3). The *Confusion Assessment Method (CAM)* will be used to assess for delirium throughout the first three postoperative days using previously described methods.^{14,40} Lastly, a follow-up health and well-being survey will be sent to participants thirty days after surgery. This survey will include the Veterans RAND 12 Item Health Survey (VR-12, continuous measure).⁵² Presence of persistent opioid use (yes/no, binary) will also be asked in this thirty-day survey.

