6 STUDY PROCEDURES

6.1 Screening Visit

For initial screening visits, patients will be seen during preoperative clinic visits. The study coordinator will review the study details with potential participants, and informed consent will be obtained after confirming eligibility criteria are met. Depending on when a preoperative clinic visit is scheduled in relation to surgery, the timeframe from enrollment to drug administration may vary significantly (days-to-weeks). The goal will be to recruit patients whose surgeries are scheduled for the morning, so as to minimize the likelihood of administering caffeine late in the afternoon. See "Schedule of Activities" for full list of procedures that will occur at this visit and all subsequent visits. Assessments, testing, and measures are described in detail in the above "Study Design" section.

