6.2 Treatment Study Period

6.2.1 Visit 1 (Day 1)

As outlined in the above protocol, visit 1 (day 1) will be the day of scheduled surgery. During this time, a preoperative pregnancy test will first be drawn as clinically indicated. Vitals will be taken throughout the perioperative period per clinical guidelines and protocols. The RCSQ will be administered to assess sleep quality the prior evening. Baseline Trail Making Test (TMT) scores will be collected. The wireless EEG cap will then be placed preoperatively, and EEG monitoring will then commence perioperatively under supervision of the study team. A member of the study team will then receive the study drug from the research pharmacy, which will prepare the drug per block randomization protocol. The study team will then administer this during (one-hour infusion) at the beginning of surgical closure. The EEG cap will be removed after postanesthesia care unit (PACU) arrival, and one hour after the infusion has finished, the study team will perform the designated research study assessments (i.e., pain assessments, cognitive function testing, and Quality of Recovery (QoR) questionnaire). Intraoperative and PACU opioid data will also be tabulated.

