6.2.3 Follow-up (Postoperative Days 4-7)

During this time, opioid consumption and caffeine intake assessments will be obtained over the telephone. Adverse events will continue to be monitored.

SCHEDULE OF ACTIVITIES

	Screen	Visit 1 Day 1	Visit 2 Day 2	Visit 3 Day 3	Visit 4 Day 4	Phone call Days 5-7	Day 30
Protocol Activity		Day of Surgery	POD1	POD2	POD3	POD4-7	
Visit (POD1-3) /Phone call (POD4-7)	-	X	X	X	X	X	
Informed consent	X						
Medical history	X						
Vitals*	X	X	X	X	X		
Depression, Anxiety, and Affect Scales	X			X			
Serum pregnancy test		X					
Randomization		X					
Treatment with study agent		X					
Opioid use assessments		X	X	X	X	X	
Cognitive function testing	X	X^{\dagger}					
Pain/sleep assessments [‡]	X	X	X	X	X		
Caffeine intake assessment	X		X	X	X	X	
EEG assessments		X			·		
Adverse event assessment	_	X	X	X	X	X	
Health and well-being survey							X

^{*} Vitals will be recorded per clinical protocol on each respective ward/ICU. †Second cognitive function testing session will occur in the postanesthesia care unit ‡Pain and sleep assessments will occur and twice daily (morning and afternoon) from POD1-3; the RCSQ in particular will be administered on Day 1, preoperatively. Pain assessments will also be taken once in the postanesthesia care unit prior to the cognitive function assessment. POD = postoperative day, TMT = trail making test, EEG = electroencephalogram

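### The baseline Trail Making Test has two different dates in the protocol, and the default change-score test is unadjusted with no settled rule for missed baselines

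*Combined protocol and SAP*

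**What the plan says.** **Timing.** Section 3 (Perioperative and anesthetic procedures) states: "On the day of surgery, baseline cognitive function testing (TMT) will take place in the preoperative holding area". Section 6.2.1, describing the day of surgery, agrees: "Baseline Trail Making Test (TMT) scores will be collected", before the EEG cap goes on. The Schedule of Activities has a row labelled "Cognitive function testing" with a mark under Screen and a daggered mark under Day 1. The dagger reads: "Second cognitive function testing session will occur in the postanesthesia care unit". Section 6.1 refers the reader to that schedule for the procedures at every visit, and says that enrolment may precede drug administration by days to weeks.

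**Endpoint and test.** Section 2.2.2 lists "Change in Trail Making Test scores (n) from baseline" as a secondary endpoint. Section 9.2.4 tests continuous secondary endpoints by t-test or Mann-Whitney and names no baseline covariate. It also allows modelling like that for the primary endpoint, but gives no criterion for when.

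**Missing baselines.** Section 3 (Neurocognitive assessments) warns that time pressure before surgery may prevent a baseline in some patients, and says "final standardized scores (n) will also be calculated and reported in the event that baseline scores are unable to be obtained". Section 9.2.2 has a general rule: complete-case analysis is considered below 20% missing, and multiple imputation is used above 20%.

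**The concern.** The TMT is the only cognitive performance test among the endpoints, and its endpoint is defined by reference to a baseline. If the protocol gives two dates for that baseline, the change score has no single meaning. A score taken in clinic days to weeks beforehand is a different reference from one taken in the holding area on the day of surgery. Staff working from the schedule and staff working from the text could collect different things.

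The second issue is the analysis. A change score cannot be formed without a baseline, and the protocol itself expects some to be missed. The plan offers up to four routes: complete-case change, final score, imputation and modelling. It does not say which one is the result. That choice would then be made after the data are seen. The default route also discards PACU scores that were collected, and it does not use the baseline as efficiently as a covariate would.

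**Working it through.** **1. Timing, side by side**

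| Source | First TMT | Second TMT |
|---|---|---|
| Section 3 | Day of surgery, preoperative holding | One hour after the infusion ends |
| Section 6.2.1 | Day of surgery, before the EEG cap | One hour after the infusion ends |
| Schedule of Activities | Screen | Day 1, PACU (dagger) |

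The schedule's Day 1 mark is used up by the PACU session, so its first session can only be the one under Screen. The schedule does annotate another preoperative Day 1 task (the sleep questionnaire), but it has no such note for the TMT.

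**2. The plan's own power figure**

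The documents give no power figure for the TMT. The only one, in Section 9.1, is 83% for opioid consumption with 60 patients. With 30 per arm, a difference of 6.5 − 0.7 = 5.8, SDs of 3 and 10, and two-sided alpha 0.05 (assumed), the noncentrality is 5.8/√((9+100)/30) = 3.04 on 34.2 df. Welch power is then 84.0%, so the figure reproduces. It does not bear on this point.

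**3. Precision of the TMT comparison**

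The missing share m and the baseline-PACU correlation r are not in the documents; both are assumed. Further assumptions are equal SDs at the two occasions, baselines missing at random, and a PACU score for every patient. Variances of the arm contrast are relative to the unadjusted final score in everyone, which is set to 1.

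- Change, complete case: 2(1−r)/(1−m)
- Final score, unadjusted, everyone: 1
- Final score adjusted for baseline, everyone, missing baselines mean-filled: (1−m)(1−r²) + m

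At m = 20%:

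| r | Change | Final | Adjusted | Lower than change by | Lower than the better of change and final by |
|---|---|---|---|---|---|
| 0.5 | 1.25 | 1.00 | 0.80 | 36% | 20% |
| 0.6 | 1.00 | 1.00 | 0.71 | 29% | 29% |
| 0.7 | 0.75 | 1.00 | 0.61 | 19% | 19% |
| 0.8 | 0.50 | 1.00 | 0.488 | 2% | 2% |
| 0.85 | 0.375 | 1.00 | 0.422 | change is better | change is better |

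The two curves cross where 2.5(1−r) = 1 − 0.8r², that is 0.8r² − 2.5r + 1.5 = 0. This gives r = (2.5 − √1.45)/1.6 = 0.81.

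Reduction against complete-case change for other missing shares:

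| m | r = 0.5 | r = 0.6 | r = 0.7 | r = 0.8 |
|---|---|---|---|---|
| 0% | 25% | 20% | 15% | 10% |
| 10% | 30% | 24% | 16% | 5% |
| 30% | 42% | 35% | 23% | 3% |

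The 30% row is only for scale, because Section 9.2.2 would impute there.

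**4. In terms of power**

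With N = 60, complete-case change loses 6, 12 or 18 patients at m = 10%, 20% or 30%. At m = 20%, the difference detectable with 80% power is (1.96 + 0.84)·√(2/30 × relative variance), in final-score SDs:

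- r = 0.5: change 0.81, final 0.72, adjusted 0.65
- r = 0.7: change 0.63, final 0.72, adjusted 0.56

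Power for a 0.7 SD difference at m = 20%, by normal approximation and then by simulation (10,000 runs, mean fill):

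- r = 0.5: change 68% (66%), final 77% (76%), adjusted 86% (84%)
- r = 0.7: change 88% (86%), final 77% (76%), adjusted 93% (92%)

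**The case against.** A reader might infer that every patient with a missed baseline is lost from the cognitive results. The documents do not support that. The sentence in Section 3 is itself a fallback that reports final scores. Section 9.2.2 imputes above 20% missing. The longitudinal model in Section 9.2.3 has a baseline level of time and a subject intercept; if carried over to the TMT, it would keep a patient who has only a PACU score. What survives is narrower. The scope of the final-score fallback is unclear, complete case below 20% is only considered, exactly 20% has no rule, and the modelling is optional. No order of precedence is given.

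A reader might also infer that baselines will in fact be mixed, some from clinic and some from the holding area. The documents contradict each other, but they do not say that this will happen, and any added noise cannot be quantified from them.

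The word second in the schedule's footnote could mean the second session of Day 1. That would make three sessions (Screen, holding, PACU) against the two described in Section 3. It would also leave open which of the two earlier scores is the baseline, so the conflict is not removed.

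Finally, adjustment with mean fill is not always more precise than change. At 20% missing its advantage nearly vanishes at r = 0.8 and reverses above about 0.81. That limit stands. The TMT is also one of eight secondary endpoints in a Phase II trial whose synopsis states a feasibility objective.

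**Conclusion.** The timing contradiction follows directly from the documents and needs no assumptions: the schedule and the text must be reconciled to one baseline occasion.

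The analysis point holds in limited form. By default the TMT change score is compared without baseline adjustment. Patients with a missed baseline leave that comparison when complete-case analysis is used, and the alternatives are conditional and unranked. With 20% of baselines missing and r between 0.5 and 0.7, adjusting the PACU score for baseline lowers the variance of the arm contrast by 19-36% against complete-case change. The reduction is about 19-29% against the better of change and unadjusted final score. These sizes rest wholly on the assumed missing rate and correlation. This is a worthwhile, low-cost improvement to a secondary endpoint; it does not threaten the primary analysis.

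**What to change.** 1. Edit the schedule or the text so that both give the same single baseline TMT occasion for all patients. If a test at both screening and the day of surgery is intended, say which one is the baseline and whether the other may stand in when it is missed.
2. In Section 9.2.4, make the main TMT analysis the PACU standardised score in all patients who have one, with baseline TMT as covariate.
3. Prespecify how a missing baseline is handled, for example overall mean fill plus a missing indicator (acceptable because the baseline precedes the blinded infusion), or the multiple imputation already planned. Apply it whatever the missing rate, so that the 20% boundary no longer matters. State separately how patients without a PACU score are handled.
4. Report change scores descriptively.

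The cost is one schedule edit and a few sentences of SAP wording. No new data are needed.

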7.2 Secondary and Tertiary Assessments

Secondary Outcomes

- •VAS scores (n)
- •BPS scores (n)
- •Time to anesthetic emergence (min)
- •Change in TMT scores (n)
- •Delirium incidence (%)
- •Postoperative depression screen incidence (%)
- •Postoperative anxiety screen incidence (%)
- •Change in affect scores (n)

Tertiary Outcomes

- •EEG spectral power (decibels, dB)
- •EEG connectivity (e.g., phase lag index, PLI)
- •Daily number of caffeinated beverages (n) to compare overall caffeine intake between the two groups throughout the study period (as a potential confounding/mediating variable).
- •Preoperative sleep quality, via Richards-Campbell Sleep Questionnaire (continuous measure, n) as a potential confounding/mediating variable.

- •New self-reported sleep disturbances (n) in each group
- •Opioid use (mg), postoperative days 4-7
- •Opioid use (yes/no) at 30 days
- •Patients-reported health and well-being scores (n) Veterans RAND 12 Item Health Survey (VR-12, continuous measure)⁵² at 30 days

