9.2.4 Analysis of Secondary Endpoints

For secondary endpoints, continuous data will be analyzed using Student's t-test or Mann-Whitney U test, as appropriate. Categorical data will be analyzed using chi-squared or Fisher's Exact tests, as appropriate. Modeling will be performed similar to the above primary endpoint description if appropriate.

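### HADS is collected at baseline, but the only committed depression and anxiety comparison is an unadjusted postoperative share scoring 8 or more, with incidence left undefined

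*Combined protocol and SAP*

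**What the plan says.** Section 3 (Neuropsychological assessments) schedules HADS twice: "These assessments will take place at baseline and after the last inpatient assessment on postoperative day 3". It sets the cut-off: "Scores ≥8 for the anxiety (HADS-A) and depression (HADS-D) subscales will be considered positive screens".

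Section 2.2.2 lists the endpoints as "Positive depression screen incidence" and "Positive anxiety screen incidence", each in percent. Section 7.2 restates the first as "Postoperative depression screen incidence" and words anxiety the same way. For the test, Section 9.2.4 says: "Categorical data will be analyzed using chi-squared or Fisher's Exact tests, as appropriate". It then adds that modelling like that of the primary endpoint will be done where suitable, without naming an endpoint, a covariate or a trigger.

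Two other passages bear on the point. Section 9.2.2 brings measures with a standardized difference above 0.1 into the multivariable models. Section 9.2.3 describes a longitudinal model whose time factor includes a baseline level. Neither mentions HADS.

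Other endpoints are specified more fully. Affect (PANAS, taken at the same visits as HADS) and the Trail Making Test are analysed as change. For sleep, Section 7.2 restricts the count to new cases: "New self-reported sleep disturbances (n) in each group".

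**The concern.** Objective C in Section 2.1 is about recovery: the hypothesis is that caffeine improves mood and reduces signs of depression. A postoperative share above a threshold addresses this only indirectly. A patient who falls from 15 to 9, or rises from 0 to 7, does not change category. The baseline score, which could sharpen the comparison, has no assigned use.

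The word incidence adds an ambiguity. If it means all positive screens after surgery, a patient scoring 10 before and 10 after is counted, and the quantity is a prevalence. If it means new positives, patients positive at baseline leave both numerator and denominator. The two readings give different percentages and different sample sizes, and the plan does not choose.

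At stake is the precision and interpretability of two of the eight secondary endpoints. The primary opioid analysis is not affected.

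**Working it through.** **The plan's own figures.** The documents give no power, positive-screen rate, standard deviation or baseline correlation for HADS. The only stated power, 83% with 60 patients, concerns opioid use. It reproduces: difference 6.5 − 0.7 = 5.8; standard error √((9 + 100)/30) = 1.91; Satterthwaite df 34.2; Welch power 84% at a two-sided 0.05 level (level assumed). It says nothing about HADS.

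**Inputs.** From the documents: 30 per arm (Figure 2), cut-off 8, two HADS time points, chi-squared or Fisher. Assumed: share positive p = 20–30%; baseline/follow-up correlation r = 0.3–0.6; normally distributed scores.

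**Information kept by the planned test.** Dichotomising a normal score keeps φ(z)²/[p(1 − p)] of the information, where z is the cut-off in SD units and φ is the normal density. Baseline adjustment reduces the residual variance to (1 − r²). The unadjusted binary test therefore keeps the product of the two, relative to ANCOVA on the score.

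- p = 0.2: z = 0.842, φ(z) = 0.280, so 0.280²/0.16 = 0.49.
- p = 0.3: z = 0.524, φ(z) = 0.348, so 0.348²/0.21 = 0.58.

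| r | 1 − r² | p = 0.2 | p = 0.3 |
|---|---|---|---|
| 0.3 | 0.91 | 0.45 | 0.52 |
| 0.5 | 0.75 | 0.37 | 0.43 |
| 0.6 | 0.64 | 0.31 | 0.37 |

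The range is 31–52%. Multiplying by 60, the planned test does the work of about 19 to 31 patients analysed by ANCOVA. Most of the loss comes from the dichotomy; the baseline adds to it as the correlation rises.

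**The same point as power.** For an assumed true effect of 0.5 SD, 30 per arm, placebo share 20–40% and r = 0.5–0.7 (1,500 simulated trials per setting, Monte Carlo error about 1.3 percentage points):

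| Analysis | Power |
|---|---|
| Share ≥8, Fisher | 12–23% |
| Share ≥8, chi-squared | 22–31% |
| Follow-up score, no baseline | 47–49% |
| Follow-up score, ANCOVA | 59–76% |

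At r = 0.3 the normal approximation for ANCOVA gives 0.5/√(0.91 × 2/30) − 1.96 = 0.07, a power of about 53%. With a weak correlation the gain from adjustment itself is therefore small.

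**Exposure to chance imbalance.** The between-arm difference in baseline-positive share has SD √(2p(1 − p)/30), which is 10 percentage points at p = 0.2 and 12 at p = 0.3. Under simple binomial sampling the arms differ by three or more baseline positives in about 42–48% of trials. Section 3 stratifies on age and gender only, so nothing balances baseline HADS directly. How much of an imbalance carries through depends on the correlation between baseline and follow-up status, which is 0.16–0.39 under these assumptions. A one-SD imbalance then shifts the expected follow-up difference by about 2 points (0.16 × 10) to 5 points (0.39 × 12).

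**Share of follow-up positives already positive at baseline.** Under the same model this is 33–43% at r = 0.3 and 44–58% at r = 0.5–0.6. The choice between the two readings of incidence is therefore not trivial.

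**The case against.** A reader might infer that the planned result mainly reflects who was positive before surgery, or that it is biased. The documents do not support either. Allocation is randomized 1:1, so baseline status is balanced in expectation and the unadjusted test is valid. Under r = 0.5–0.6, baseline status explains only about 9–16% of the variance in follow-up status, and roughly half of follow-up positives are new.

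A reader might also infer that the plan definitely counts baseline positives as incident cases. No text says so. Incidence ordinarily means new cases, and the collected baseline would identify them. Against that, Section 7.2 says new for sleep and does not say it for HADS. The wording is ambiguous, and the defect is the missing definition.

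It is also fair to say that the plan does not rule out using the baseline. The modelling sentence in Section 9.2.4 could extend the Section 9.2.3 model, with its baseline time level, to HADS. The imbalance rule in Section 9.2.2 could bring the score in: at 30 per arm a standardized difference above 0.1 arises by chance about 70% of the time (SD of the difference √(2/30) = 0.26). But the first route has no stated trigger, and the second applies only to multivariable models, which the committed HADS test is not. The accurate description is that baseline use is not pre-specified for HADS.

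Finally, PANAS already gives a change analysis for affect, the cut-off of 8 is a referenced screening threshold, and no power is claimed for HADS in a Phase II trial whose synopsis states a feasibility objective. All of this stands and limits the importance of the point. It does not explain why a baseline collected for HADS has no stated role.

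**Conclusion.** The point holds as an under-specified analysis with an available gain in precision. The plan commits HADS to an unadjusted comparison of postoperative positive screens, assigns the baseline score no role in it, and leaves open whether patients already positive are counted.

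The comparison is valid. Its cost is lost precision, exposure to chance imbalance at about 30 per arm, and a percentage whose denominator is undefined. The 31–52% information figure is illustrative: it rests entirely on an assumed 20–30% positive rate, a correlation of 0.3–0.6 and normal scores. HADS subscales are bounded integers and often skewed, so the true figure could differ. Because these are secondary endpoints without stated power, this is an improvement worth making before analysis and not a threat to the trial's main conclusion.

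**What to change.** In Section 9.2.4, name the HADS analysis: compare follow-up HADS-A and HADS-D scores between arms by ANCOVA, with the baseline score of the same subscale as covariate, and report the adjusted difference with its confidence interval.

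Keep the share scoring 8 or more as a reported outcome. If a test is wanted, use logistic regression adjusting for the baseline score. With 20–30% positive among 60 patients there would be only 12–18 events, so this should be supporting.

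In Sections 2.2.2 and 7.2, state what incidence means, and tabulate the postoperative screen by baseline screen status so that newly positive patients appear separately from those positive before surgery.

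The cost is SAP wording; both scores are already collected. The small downside is that the headline HADS result becomes a score difference, with the clinical cut-off kept as a supporting report.
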